### C.7.2. Windows for measurements

To ensure adequate time for patients obtaining maximum tolerated dose of carvedilol prior to visit 6 and visit 12 exercise testing, visits 1,2,3,4,7,8,9,10 and will occur as outlined  $\pm$  7 days. Visit 5 and 11 will occur as outlined  $\pm$  14 days. Visit 6 and visit 12 will occur as outlined  $\pm$  14 days.

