#### **C.5.4 Indications for Permanent Discontinuation of Study Drug**

- Intolerance to study drug
- Continued administration of study drug felt to be not indicated by the attending cardiologist or study investigator
- Pregnancy or planned pregnancy
- Other adverse events that require discontinuation of study drug in the judgment of the study investigator

The reason and the circumstances for permanent discontinuation of study drug will be documented. If study drug is permanently discontinued, the subject will continue to be followed and undergo expected tests and measurements through the planned completion date (31 weeks after randomization), unless an indication for withdrawal from trial is met.

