#### **C.6.2.b Protection Against Risks**

To minimize the potential risks listed in Section C.6.1 the following steps will be taken:

1. The starting doses of carvedilol will be low and will be up-titrated carefully (see Table 1).
2. Subjects with known renal dysfunction will be excluded from the study.
3. Blood draws, to the extent possible, will be performed after the application of a topical anesthetic cream.
4. Serum creatinine, BNP, hemoglobin, hematocrit, AST and ALT will be measured as during the screening phase. Serum creatinine, BNP, AST and ALT will be measured during the treatment phase (Table 5).
5. Pregnancy or a planned pregnancy during the trial are exclusion criteria. A urine pregnancy test will be obtained during the screening phase. A statement regarding the potential risk of one of the study drugs will be given to female subjects of child-bearing potential and to the parents of female subjects less than 18 years of age. They will be asked questions about the subject's sexual activity. In addition, this risk is listed in the consent and the assent. Written documentation of birth control measures will be required for female subjects who are sexually active.
6. The study sponsor will pay for all testing that is not part of routine care.

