#### **C.6.6.c Identification of and Data Collection Procedures for Adverse Events**

In this trial, a primary safety concern as well as one of the secondary end points is to capture and compare adverse drug reactions between carvedilol versus placebo. In addition, following standard clinical trial procedures, information on other adverse events will be collected.

*Adverse drug reactions* will be assessed at baseline, at the end of up-titration, and at each study visit through a standardized questionnaire that will be administered by the study coordinators or investigators. The assessment at baseline will be obtained while the subject is not taking any study drug and is essential to accurate assessment of drug effects. *Adverse events* that are not considered adverse drug reactions will be identified when they are reported to the clinical center or during scheduled study visits by study coordinators and investigators. Subjects and families will be encouraged to report any serious event to study personnel as soon as the event occurs, rather than waiting for scheduled visits.

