**Table 5. Treatment Phase Measures**

Treatment Period 1 (week 0-12)						
	Visit 1 (week 0)	Visit 2 (week 1)	Visit 3 (week 2)	Visit 4 (week 3)	Visit 5** (week 8)	Visit 6 week 12
Duration (hrs)	1-1.5	<1	<1	<1	<1	2
Vital signs	x	x	x	x		x
NYHA HF Classifications	x	x	x	x		x
Adverse Drug Effect	x	x	x	x	x	x
Compliance Check		x	x	x	x	x
Safety Labs (CMP, BNP, CBC)	X					x
Exercise Test	x*					x
Study Drug Medication	X_initiate	X- uptitration 1	X- uptitration 2	X-no change		X-after visit stop study medication***
Washout Period (Week 13-18)						
Treatment Period 2 (week 19-30)						
	Visit 7 (week 19)	Visit 8 (week 20)	Visit 9 (week 21)	Visit 10 (week 22)	Visit 11** (week 26)	Visit 12 (week 30)
Duration (hrs)	2	<1	<1	<1	<1	2
Vital Signs	x	x	x	x		x
NYHA HF Classifications	x	x	x	x		x
Adverse Drug Effect	x	x	x	x	x	x
Compliance Check	x	x	x	x	x	x
Safety Labs (CMP, BNP, CBC)	X					x
Exercise Test	x					x
Study Drug Medication	X-initiate	X- uptitration 1	X- uptitration 2	X-no change		after visit stop study medication***

\*-exercise test from screening phase may be used if visit 1 exercise test if done within 14 days of visit 1,

\*\*-may be phone visit

\*\*\*dose of study medication decreased during weeks 6 and 31 and then stopped

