**Response to Bradycardia or Hypotension:**

1. Heart rate and/or blood pressure will be confirmed by two repeat measures after initial measurement with at least 5 minutes between measurements, the average of all three measurements will be recorded
2. The study investigator will reduce the dose of study drug back to previously tolerated dosing
3. If hypotension or bradycardia develop after initiation prior to uptitration, study drug will be stopped

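### The plus or minus 7 day window on the weekly dose-step and check visits equals their spacing and no minimum time on a dose is set, so a step or check after 2 days is in window

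*Combined protocol and SAP*

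**What the plan says.** Table 5 starts study drug at Visit 1 (week 0), raises the dose at Visits 2 and 3 (weeks 1 and 2) and leaves it unchanged at Visit 4 (week 3). Period 2 repeats this at Visits 7 to 10 (weeks 19 to 22). C.7.2 then states that "visits 1,2,3,4,7,8,9,10 and will occur as outlined" with a tolerance of 7 days either way. The reason given is "To ensure adequate time for patients obtaining maximum tolerated dose of carvedilol prior to visit 6 and visit 12 exercise testing".

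On the pace of titration, the first protection listed in C.6.2.b is "The starting doses of carvedilol will be low and will be up-titrated carefully (see Table 1". Both that section and C.5.3.1 refer to Table 1, which gives doses by weight band and no timing. How long each dose is held therefore follows only from Table 5 read with C.7.2.

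The safeguards around each step are these:
- Vital signs, NYHA class and adverse drug effects are recorded at every dose-step visit and at Visits 4 and 10 (Table 5).
- Adverse drug reactions are assessed at baseline, "at the end of up-titration, and at each study visit through a standardized questionnaire" (C.6.6.c).
- For bradycardia or hypotension, C.7.4 says "The study investigator will reduce the dose of study drug back to previously tolerated dosing", and also "If hypotension or bradycardia develop after initiation prior to uptitration, study drug will be stopped". C.7.6 has a similar reduction rule for symptoms attributed to the drug.
- C.5.4 lists "Intolerance to study drug" among the grounds for permanent discontinuation, together with the judgment of the investigator or attending cardiologist.

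**The concern.** A window as wide as the spacing lets neighbouring visits come close together or coincide. At Visits 2, 3, 8 and 9 the visit date is also the date of a dose increase. The protocol specifies what is checked before an increase, but not how much exposure the check must cover. A check after 2 days on a dose says less about tolerance than one after 7 days, so the previously tolerated dose to which C.7.4 and C.7.6 return is less well established.

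Visits 4 and 10 are the first look at the top dose and carry the same window. The next contact after each, Visit 5 or 11, may be by phone and has no vital signs in Table 5. The next scheduled vital signs are then at Visit 6 or 12.

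The purpose stated in C.7.2 is enough time at the maximum tolerated dose before the exercise tests. That calls for a latest date for each step. It does not call for shorter intervals between steps.

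**Working it through.** **Inputs.** Visit weeks from Table 5; windows of plus or minus 7 days (dose-step and check visits) and plus or minus 14 days (Visits 6 and 12) from C.7.2; twice-daily dosing from C.5.3.1; doses from Table 1.

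**Scheduled spacing.** One week between consecutive visits is 7 days, or 7 x 2 = 14 doses.

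**Windows in days from week 0.**

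| Visit | Action | Nominal day | In-window days |
|---|---|---|---|
| 1 | initiate | 0 | -7 to 7 |
| 2 | up-titration 1 | 7 | 0 to 14 |
| 3 | up-titration 2 | 14 | 7 to 21 |
| 4 | no change | 21 | 14 to 28 |
| 7 | initiate | 133 | 126 to 140 |
| 8 | up-titration 1 | 140 | 133 to 147 |
| 9 | up-titration 2 | 147 | 140 to 154 |
| 10 | no change | 154 | 147 to 161 |

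**Shortest gap.** For spacing 7 and window w, the shortest gap is 7 - 2w. With w = 7 this is -7, so neighbouring windows overlap (Visits 2 and 3 share days 7 to 14) and impose no positive minimum.

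**Examples in window.**
- Visit 2 on day 12, Visit 3 on day 14: 14 - 12 = 2 days, 2 x 2 = 4 doses.
- Visit 7 on day 138, Visit 8 on day 140: 140 - 138 = 2 days, 4 doses.
- Check on the top dose: Visit 3 on day 19, Visit 4 on day 21: 21 - 19 = 2 days, 4 doses.

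**Smaller slips.** If the earlier visit is k days late and the next is on its nominal date, the gap is 7 - k days and 2(7 - k) doses: k = 2 gives 5 days (10 doses), k = 3 gives 4 days (8 doses), k = 5 gives 2 days (4 doses).

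**Choice of anchor.** C.7.2 does not say whether the window runs from the calendar schedule or from the previous visit. Counted from the previous visit, 7 plus or minus 7 gives 0 to 14 days, so a 2-day gap is allowed either way. The first example also stands if Visit 1 is fixed at day 0.

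**Size of a step.** Table 1 has four weight bands with two steps each. Seven of the eight steps double the dose (3.125/1.56 within rounding). The exception is 9.375/6.25 = 1.5, in the band from 30 to under 40 kg.

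**Time left before the exercise test.** From the latest in-window up-titration 2 to the earliest in-window test: period 1, (84 - 14) - 21 = 49 days; period 2, (210 - 14) - 154 = 42 days.

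**Does a 7-day minimum fit?** From the latest permitted starts: 7 + 7 = 14, 14 + 7 = 21, 21 + 7 = 28; and 140 + 7 = 147, 147 + 7 = 154, 154 + 7 = 161. Each result equals the present outer limit for that visit, so the limits stand and the 49 and 42 days are unchanged.

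**The case against.** What a window permits is not what sites do. The 2-day example needs one visit 5 days late and the next left on its nominal date, and nothing in the documents suggests that staff would schedule this way. No dose rises automatically: drug is dispensed at the visit, after the checks, and the investigator can hold back, reduce or stop. C.5.3.5 adds further monitoring after an adverse reaction. The documents give no half-life, time to steady state or time to onset of hypotension or bradycardia, so they do not show that 2 days is too short or that any particular minimum is right.

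Most of this stands. It limits the point to a modest improvement and means that any minimum shorter than the scheduled 7 days would be a clinical choice. It does not remove the gap: the checks are required, the time on dose before them is not, and a compressed step would be in window.

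A reader might go further in three ways that the documents do not support:
- *Same-day increases are intended.* The arithmetic allows a gap of 0 days, but Table 5 sets separate weekly visits, each with its own checks. The overlap looks like a side effect of the window, not a plan.
- *Early steps would trigger the wrong response in C.7.4.* One could suppose an event caused by the initial dose that appears after an early first increase and leads to stepping back where the weekly schedule would have led to stopping. Once the dose has been raised, that cause cannot be identified, stepping back is reasonable, and C.5.4 still allows stopping.
- *The efficacy comparison suffers.* At least 42 days remain between the last step and the exercise test.

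**Conclusion.** The point holds as a minor matter of dosing conduct and tolerability. C.7.2 allows a dose increase, or the check on the top dose, 2 days (4 doses) after the previous step where Table 5 schedules 7 days (14 doses), and no other section prevents it. Seven of the eight increases in Table 1 are doublings, and careful up-titration is the first risk protection that the protocol lists.

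The conclusion rests on the Table 5 weeks and the C.7.2 tolerance as written, and does not depend on how the window is anchored. That a shorter time on a dose gives a weaker check is a general judgment, not a figure from the documents. How often visits would be compressed is unknown, because no visit-timing data are given. The primary endpoint and the sample size are not affected. The change is worth making at the next amendment but is not essential.

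**What to change.** Add one sentence to C.7.2: Visits 2, 3, 4, 8, 9 and 10 take place no sooner than a fixed minimum number of days after the actual date of the previous dose step, and no later than the present outer limits. Visits 4 and 10 belong in the sentence because the check on the top dose has the same window.

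The natural minimum is the 7 days that Table 5 already schedules. A shorter one, such as 5 days, would be for the sponsor to justify clinically, since the documents give no source for it. Visits 6 and 12 need not move.

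The cost is flexibility: a late step delays the next one. With a 7-day minimum, a Visit 1 that is s days late (0 to 7) leaves days 7 + s to 14 for Visit 2, a slack of 7 - s days. After a latest-possible start the slack is zero, and Visits 2, 3 and 4 must fall exactly on days 14, 21 and 28 (Visits 8, 9 and 10 on days 147, 154 and 161). With a 5-day minimum, the same start would leave days 12 to 14 for Visit 2.

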### **C.7.3. Exercise Testing**

All Exercise Tests for study purposes will be performed at the Children's Medical Center of Dallas. Studies will be performed by experienced pediatric EKG technicians and exercise physiologists. An attending cardiologist will be immediately available per institutional protocol for any adverse event experienced during the exercise test. The exercise test will provide peak oxygen consumption, peak heart rate, ventilatory efficiency of carbon dioxide as well as submaximal exercise test performance. As previously described these data are associated with outcomes in the SV population and therefore were chosen as the primary and secondary endpoints. Exercise tests will be performed on Visit 1, 6, 7, and 12.

### **C.7.4. Vital Signs**

Vital signs will include heart rate, blood pressure and pulse oximetry. Vital signs will be obtained by a pediatric research coordinator or appropriate designee. As previously described, bradycardia and hypotension are possible adverse events of treatment with carvedilol.

#### **Bradycardia will be defined as:**

1. Heart rate that is less than two standard deviations below age normal that is associated with at least one of the following:
  1. New symptoms of syncope, pre-syncope, lightheadedness, dizziness or nausea
  2. Hypotension
  3. Heart block (2nd or 3rd degree)
  4. New symptoms of dyspnea, fatigue or palpitations
  5. Development of any new symptom that is deemed to be due to bradycardia by a study investigator

#### **Hypotension will be defined as:**

1. For patients < 18 years of age, systolic and/or diastolic blood pressure less than 2 standard deviations from the age/sex/height normal values; for patients 18 years of age or older a systolic blood pressure of less than

85mmHg and/or diastolic blood pressure of less than 55 mmHg; and is associated with at least one of the following:

1. Syncope, pre-syncope, dizziness, lightheadness or nausea
2. Newly developed bradycardia
3. Heart block
4. New symptoms of dyspnea, fatigue, or palpitations
5. Development of any new symptom that is deemed to be due to hypotension by a study investigator

**Response to Bradycardia or Hypotension:**

1. Heart rate and/or blood pressure will be confirmed by two repeat measures after initial measurement with at least 5 minutes between measurements, the average of all three measurements will be recorded
2. The study investigator will reduce the dose of study drug back to previously tolerated dosing
3. If hypotension or bradycardia develop after initiation prior to uptitration, study drug will be stopped

**C.7.5. NYHA Classification**

New York Heart Association classification of heart failure symptoms is a frequently used method of classifying the degree of heart failure symptoms a patient is experiencing. The NYHA classification is shown below in Table 6. The classification will be assessed on visits 1, 2, 3, 4, 6, 7, 8, 9, 10, 12. It will help objectively measure the degree of heart failure symptoms and the response of heart failure symptoms to carvedilol versus placebo in the study population. NYHA classification will be assessed by the principal investigator, study investigator, research coordinator or appropriate designee.

Table 6. NYHA Heart Failure Symptom Classification

NYHA Class	Symptoms
I	Cardiac disease, but no symptoms and no limitation in ordinary physical activity, e.g. no shortness of breath when walking, climbing stairs etc.
II	Mild symptoms (mild shortness of breath and/or angina) and slight limitation during ordinary activity.
III	Marked limitation in activity due to symptoms, even during less-than-ordinary activity, e.g. walking short distances (20–100 m). Comfortable only at rest.
IV	Severe limitations. Experiences symptoms even while at rest . Mostly bedbound patients.

### C. 7.6. Adverse Drug Reaction Screening

At all study visit, the principal investigator, study investigator, research coordinator or other appropriate designee will assess the presence of possible side effects from carvedilol. The study participant will be screened for the presence of the following symptoms: dizziness, syncope, palpitations, fatigue, lethargy, mood changes, behavior changes, sleep disturbances, nightmares, headache, gastrointestinal pain, nausea, emesis, constipation, peripheral edema, wheezing, shortness of breath, myalgias, back pain, cough, chest pain. CMP and BNP will be reviewed at visits 6 and 12 for presence of hepatic or renal dysfunction as previously described. If the patient is experiencing any of the listed side effects and it is felt by the study investigator and/or PI to be from the study drug, then the dose of study drug will be reduced to previously tolerated dose

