*Rationale:* Submaximal exercise capacity is directly related to cardiovascular health and has been shown to be prognostic of outcomes in cardiovascular disease.

*Measures:* Primary outcome measure will be the volume of oxygen consumption at anaerobic threshold indexed to patient weight. Secondary measures will include watts and respiratory exchange ratio at anaerobic threshold.

*Hypothesis:* Carvedilol will increase volume of oxygen consumption at anaerobic threshold.

**Secondary Aim 3:** To compare the effect of carvedilol to that of placebo on ventilatory efficiency of carbon dioxide.

*Rationale:* The ventilatory efficiency of carbon dioxide has prognostic value in patients with heart failure.

*Measures:* Primary measures will be ventilatory equivalent of carbon dioxide at anaerobic threshold ( $VE/VCO_2$  at anaerobic threshold). Secondary measure will be slope of minute ventilation to volume of carbon dioxide production ( $VE/VCO_2$  slope).

*Hypothesis:* Carvedilol will improve ventricular mechanics and therefore decrease ventilatory efficiency of carbon dioxide.

**Secondary Aim 4:** To evaluate the safety of carvedilol in Fontan patients over an intermediate time period.

*Rationale:* Limited data are available regarding the safety profile of carvedilol in the Fontan population has not been previously described.

*Measures:* Laboratory data and the number of serious adverse events and adverse events reported during the two different treatment periods (carvedilol v. placebo).

*Hypothesis:* Carvedilol will have a similar side effect profile compared to placebo.

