## **C.6. Potential Risks, Benefits, Adverse Events and Protections**

### **C.6.1. Potential Risks**

The possible risks or discomforts to the subjects include those listed below.

1. Treatment with carvedilol may rarely induce adverse drug reactions including symptomatic bradycardia, dizziness, postural hypotension, fatigue, lethargy, mental depression, headache, nausea, diarrhea, sleep disturbances, and asthma exacerbation.
3. Self-limited exercise tests pose very small risks of syncope, arrhythmias, hypotension, emesis, dizziness, leg or other muscle cramping.
4. Risks associated with drawing blood from a vein include momentary discomfort and/or bruising. Infection, excess bleeding, clotting, and fainting are also possible, although unlikely. Less than 5 ml of blood is needed for the 3 safety laboratories (CBC, CMP, and BMP).
5. Study investigators from UT Southwestern and Children's Health will have access to the medical record for 5 years after each subject completes the study to review the results of follow-up clinical course, surgical intervention, and other relevant studies.

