### *Expectedness*

The purpose of reporting is to provide new, important information on serious reactions or events previously unobserved or undocumented. Therefore, all adverse events will be evaluated as to whether their occurrence was unexpected.

1. Unexpected: An unexpected adverse event or adverse drug reaction is one for which the nature or severity is not consistent with information in the protocol, consent form, or product brochure.
2. Expected: An event is considered expected if it is known to be associated with the study drugs. For this protocol, expected events include the following:
  - a. Bradycardia
  - b. Dizziness

- c. Syncope
- d. Hypotension
- e. Palpitations
- f. Fatigue
- g. Lethargy
- h. Mood changes
- i. Behavior changes
- j. Sleep disturbances
- k. Nightmares
- l. Headache
- m. Nasal congestion
- n. Gastrointestinal pain
- o. Dysgeusia
- p. Nausea
- q. Emesis
- r. Diarrhea
- s. Constipation
- t. Myalgias
- u. Back pain
- v. Peripheral edema
- w. Wheezing
- x. Shortness of breath
- y. Cough
- z. Chest pain
- aa. Renal dysfunction
- bb. Anemia
- cc. Hepatic dysfunction

*Causality*

Causality assessment is required in clinical investigations to help determine which events require expedited reporting. The following criteria will be used to determine causality:

1. Not Related: The event is clearly related to other factors, such as the subject's clinical state, or non-study drugs or interventions.
2. Possibly Related: The event follows a compatible temporal sequence from the time of administration of the study drug, but could have been produced by other factors such as the subject's clinical state or non-study drugs or interventions.
3. Probably Related: The event follows a reasonable temporal sequence from the time of drug administration, and cannot be reasonably explained by other factors such as the subject's clinical state, or non-study drugs or interventions.

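### The adverse-reaction symptom screen leaves out three symptoms the protocol lists as expected (diarrhea, nasal congestion, dysgeusia), so they may be under-counted in both treatment periods

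*Combined protocol and SAP*

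**What the plan says.** Three places in the combined protocol and SAP list reactions to the study drug.

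- **C.6.1 (Potential Risks)** names reactions to carvedilol and ends with "headache, nausea, diarrhea, sleep disturbances, and asthma exacerbation".
- **C.6.6.b (Expectedness)** states "For this protocol, expected events include the following" and gives items a to cc. Among them are "m. Nasal congestion", dysgeusia (item o) and diarrhea (item r).
- **C.7.6 (Adverse Drug Reaction Screening)** says "The study participant will be screened for the presence of the following symptoms" and names the symptoms to be checked at all study visits. Its gastrointestinal part reads "gastrointestinal pain, nausea, emesis, constipation, peripheral edema, wheezing".

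C.6.6.c says that "one of the secondary end points is to capture and compare adverse drug reactions between carvedilol versus placebo". It collects these reactions at baseline, at the end of up-titration and "at each study visit through a standardized questionnaire". It calls the off-drug baseline assessment essential for judging drug effects. The questionnaire is not reproduced. Besides laboratory data, Secondary Aim 4 takes as its measure "the number of serious adverse events and adverse events reported during the two different treatment periods".

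**The concern.** Within one safety end point, most expected symptoms are prompted for and three are not. A prompted symptom is asked about at every visit and has an off-drug baseline. An unprompted one depends on the subject raising it or on a general enquiry by staff, and it has no solicited baseline against which a later report can be read. Counts for the three symptoms would then not be comparable with those for the other symptoms, and a real excess on carvedilol would be harder to see.

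The omission has the look of a slip. In C.6.6.b diarrhea stands between emesis and constipation. In C.7.6 the list passes straight from one to the other, and the text gives no reason.

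**Working it through.** The plan states no figure on this point, so the check compares the two lists item by item.

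**Step 1: the counts.**
- Expected events in C.6.6.b, items a to cc: 26 + 3 = 29.
- Symptoms in C.7.6: 21. All 21 also appear in C.6.6.b.
- Expected but not on the screen: 29 − 21 = 8.

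**Step 2: sort the eight.**

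| Item | How it would be found | Gap in the screen? |
|---|---|---|
| Bradycardia, hypotension | Vital signs (C.7.4) | No |
| Renal dysfunction, hepatic dysfunction | Chemistry review at visits 6 and 12 (C.7.6) | No |
| Anemia | Blood count in the Table 5 safety laboratories | No |
| Diarrhea, nasal congestion, dysgeusia | Only by asking, or if the subject mentions it | Yes |

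Section C.7.7 names the blood count only at screening, which differs from Table 5. That does not affect this point, because anemia is a laboratory finding either way.

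Symptom-type expected events: 29 − 2 − 3 = 24. Not on the screen: 24 − 21 = 3, or 3/24 = 12.5%.

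**Step 3: the visits.** Table 5 marks adverse drug effects at all 12 visits. Visit 1 precedes study drug and visit 7 follows the washout. That leaves visits 2-6 and 8-12, so five visits in each treatment period, plus the baseline.

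**Step 4: the effect on the comparison.** Let p_C and p_P be the true incidences of one of these symptoms on carvedilol and on placebo, and c the share of events captured without prompting. Assume c is the same in both periods, which is reasonable under masking with the same screen in each.

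- Observed difference = c·p_C − c·p_P = c × (p_C − p_P)
- Observed ratio = (c·p_C)/(c·p_P) = p_C/p_P, unchanged in expectation

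The documents give no value for c. Over an assumed range of 0.25 to 0.75, 25-75% of the true absolute difference is seen.

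**Step 5: the scale in subjects.** The documents give no incidence for these three symptoms, so both the incidence and c are assumed. Expected subjects counted in one period = 30 × p × c:

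| Assumed true incidence p | c = 1 | c = 0.75 | c = 0.50 | c = 0.25 |
|---|---|---|---|---|
| 2% | 0.60 | 0.45 | 0.30 | 0.15 |
| 5% | 1.50 | 1.13 | 0.75 | 0.38 |
| 10% | 3.00 | 2.25 | 1.50 | 0.75 |

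Per symptom and period, the shortfall runs from 0.60 − 0.45 = 0.15 subjects to 3.00 − 0.75 = 2.25 subjects.

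**Step 6: after the fix.** 21 + 3 = 24 items, which covers every symptom-type expected event.

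**The case against.** The strongest reply is that the screen is not the only way in. C.5.3.5 has subjects monitored for adverse events at each visit. C.7.6 opens with a general duty to look for possible side effects. C.6.6.c also picks up other adverse events when they are reported or at scheduled visits. The questionnaire could hold more items than C.7.6. This stands in part: under-counting is likely only if the questionnaire follows C.7.6, and some events would still be captured.

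It can also be said that the two lists serve different ends, one classifying events for reporting and the other screening for symptoms, and that nothing requires them to match. That is fair, and it makes the case strongest for diarrhea, which C.6.1 names as well. But C.6.6.c makes the comparison of reactions an end point, and the plan gives no reason to prompt for 21 expected symptoms and not for three.

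A third objection concerns the remedy. C.7.6 links dose reduction to the symptoms on its list, so extending that list could widen a clinical rule without anyone intending it. This stands, and the fix allows for it.

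Two stronger readings are tempting, and the documents do not support them:

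- **That the gap favours the hypothesis of a similar side effect profile.** The absolute difference shrinks, but under equal capture the ratio does not change. C.8.1 specifies models for exercise outcomes only. There is no safety test and no similarity margin, so no decision rule exists for the gap to tilt.
- **That diarrhea would also be lost because C.6.6.d exempts uncomplicated gastroenteritis.** That section governs reporting, not what is recorded on study forms, and it exempts a diagnosis rather than diarrhea as a drug reaction.

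**Conclusion.** The mismatch is certain: exactly three symptom-type expected events, out of 24, are absent from the C.7.6 screen. The consequence is conditional. If the questionnaire uses only the C.7.6 items, diarrhea, nasal congestion and dysgeusia are likely to be under-counted in both periods, and any absolute carvedilol-placebo difference for them in Secondary Aim 4 is reduced.

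The amount of the reduction cannot be fixed from the documents. The 25-75% range rests on an assumed share of volunteered events and on equal capture in both periods; no single value within it can be defended. In subjects, the likely loss is small. This is a minor point that is cheap to correct, and it does not touch the primary endpoint. Symptoms that were not asked about cannot be reliably recovered after the trial.

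**What to change.** Add diarrhea, nasal congestion and dysgeusia to the standardized adverse-reaction questionnaire, at baseline and at every visit. Reconcile the lists in C.6.1, C.6.6.b and C.7.6, and state in C.6.6.c which list the questionnaire follows.

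Because the dose-reduction wording in C.7.6 refers to its own list, the sponsor should decide separately, and state, whether that wording covers the added items. No clinical rule is proposed here.

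The cost is three more questionnaire lines and slightly more adverse-event data to record, plus the edit to the protocol text.
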